### **8.3.2 Secondary Endpoints**

#### **8.3.2.1 Pharmacokinetics**

The PK of BMS-986016 administered both alone and in combination with nivolumab will be assessed as a secondary objective using the following endpoints derived from serum concentration vs time data in Cycle 1 and Cycle 3:

Cmax	Maximum observed serum concentration
Tmax	Time of maximum observed serum concentration
Ctrough	Trough observed serum concentration
Ctau	Concentration at the end of a dosing interval (eg, concentration at 336 hours)
Css,avg	Average concentration over a dosing interval ([AUC(TAU)/tau]
AUC(TAU)	Area under the concentration-time curve in 1 dosing interval
CLT	Total body clearance
T-HALF eff _AUC	Effective elimination half-life that explains the degree of AUC accumulation observed
T-HALF eff _Cmax	Effective elimination half-life that explains the degree of Cmax accumulation observed
AI_AUC	Accumulation index; ratio of AUC(TAU) at steady state to AUC(TAU) after the first dose
AI_Cmax	Cmax accumulation index; ratio of Cmax at steady state to Cmax after the first dose
AI_Ctau	Ctau accumulation index; ratio of Ctau at steady state to Ctau after the first dose
DF	Degree of fluctuation or fluctuation index ([Cmax - Ctau]/Css,avg)

Individual subject PK parameter values will be derived by noncompartmental methods by a validated PK analysis program. Actual times will be used for the analyses.

In Part D1-Q4W, PK of nivolumab and BMS-986016 coadministered will be assessed and compared to that of FDC of BMS-986016 and nivolumab. PK will be measured using serum concentration-time data. PK of nivolumab and BMS-986016 in Part D1-Q4W and Part D1-Q2W will also be assessed.

### **8.3.2.2 *Efficacy***

The BOR, ORR, DCR, DOR, and PFS rates at prespecified time points (eg, 24 weeks) based on Investigator assessment using RECIST v1.1 will be the secondary efficacy endpoints. The efficacy endpoints based on BICR assessment, where applicable (ie, not designated as the primary), will also be the secondary efficacy endpoints.

BOR, ORR, DCR, and DOR were defined under the primary endpoints. Progression Free Survival is defined as the time from first dose to the date of first objectively documented progression, per RECIST v1.1, or death due to any cause, whichever occurs first. Clinical deterioration in the absence of objectively documented progression per RECIST v1.1 is not considered progression for the purpose of determining PFS. Subjects who die without a reported progression will be considered to have progressed on the date of their death. Subjects who did not progress or die will be censored on the date of their last evaluable tumor assessment. Subjects who did not have any on study tumor assessments and did not die will be censored on the date of first dose. Subjects who started any subsequent anticancer therapy, including tumor-directed radiotherapy and tumor-directed surgery, without a prior reported progression will be censored at the last evaluable tumor assessment prior to initiation of the subsequent anticancer therapy. The PFS rate at time T is defined as the probability that a subject has not progressed and is alive at time T following first dose.

Landmark 1-year and 2-year OS rates will be assessed as secondary efficacy endpoints in Part D.

### **8.3.2.3 *Immunogenicity***

Incidence of ADA to either BMS-986016 or nivolumab will be assessed during treatment and for up to 135 days after their last treatment in post-treatment follow-up or for a maximum of up to 24 months of treatment, whichever comes first. A baseline ADA-positive subject is defined as a subject with positive seroconversion detected in the last sample before initiation of treatment. An ADA-positive subject is a subject with at least 1 ADA-positive sample relative to baseline after initiation of the treatment.

### **8.3.2.4 *Centrally Read ECGs (Parts A and B)***

In Part A and Part B, QTc will be assessed by a central reader at follow-up Visit 1, and on Day 1 of Cycle 1 and Cycle 3 (predose and 4-hour postdose time points). These assessments will be used to address the secondary objective of assessing the effect of BMS-986016 administered alone and in combination with nivolumab on QTc.

ECGs assessed locally by the Investigator are also collected at the start of each cycle. QTc will be calculated by the Sponsor for these ECGs. However, results will be summarized separately and are not considered part of the secondary objective.

### **8.3.2.5 Safety**

#### **8.3.2.5.1 Part D1-Q4W**

The secondary endpoint in Part D1-Q4W is the incidence of AEs in the Narrow Scope MedDRA Anaphylactic Reaction SMQ occurring within 2 days after any study therapy infusion. This incidence rate will be defined similarly to the primary safety endpoint for this part of the study except that the event rate will be based on terms within the Narrow Scope SMQ rather than the Broad Scope.

The second secondary endpoint in Part D1-Q4W is the incidence of events within the hypersensitivity/infusion reaction select AE category occurring within 2 days after any study therapy infusion. The select AEs consist of a list of preferred terms (PTs) defined by the Sponsor and represent AEs with a potential immune-mediated etiology. The MedDRA PTs to be included in the hypersensitivity/infusion reaction select AE category will be updated with each new version of MedDRA prior to database lock. The list that is the most current at the time of analysis will be used. The incidence rate of hypersensitivity/infusion reaction select AEs will be defined similarly to the primary endpoint except that the event rate will be based on terms from the hypersensitivity/infusion reaction select AE category rather than the Broad Scope MedDRA Anaphylactic Reaction SMQ.

[figure not shown]
The drug-related and all-causality Grade 3 - 5 AE rate is defined as number of subjects who experienced at least 1 AE of Grade 3 or higher, or at least 1 AE of Grade 3 or higher judged to be related to study drug by the Investigator, and with onset on or after the first dose of study treatment and within 30 days of the last dose of study treatment divided by number of treated subjects.

### **8.3.3 Exploratory Endpoints**

[figure not shown]
#### **8.3.3.1 Biomarkers**

Biomarker endpoints from peripheral blood will generally be measured at multiple time points and evaluated as both predictive and pharmacodynamic markers in the context of the exploratory biomarker objectives. These may include measures such as levels and change from baseline in levels of the following at each scheduled time point:

- Serum soluble factors

Biomarker endpoints from tumor biopsies will be explored predominantly in an effort to identify baseline markers predictive of efficacy since they are only measured at baseline for most subjects. For the subset of subjects who have both pretreatment and on-treatment biopsies, pharmacodynamic associations may be explored. Endpoints may include measures such as pretreatment levels and change in levels observed on-treatment of:

Appropriate functional transformation of these exploratory measures will be applied as necessary. Measures not available at the time of the clinical study report may be summarized in a separate report.

### **8.3.3.2 *Pharmacokinetics***

Nivolumab concentration-time data at scheduled trough (Ctrough) and end-of-infusion time points will be evaluated as an exploratory endpoint. Measurements will be collected on treatment (up to 12 cycles) and for up to 135 days during the post-treatment follow-up or for a maximum of up to 24 months of treatment, whichever comes first.

### **8.3.3.3 *Efficacy***

The BOR, ORR, DCR, DOR, and PFS rates at prespecified time points will be explored by iRECIST assessments based on BICR. Landmark 1-year and 2-year OS rates will be assessed as exploratory efficacy endpoints in the study (except for Part D).

## **8.4 *Analyses***

Unless otherwise specified, data from Part A (monotherapy dose escalation) and Part A1 (monotherapy dose expansion) will be presented separately from data collected in Part B, Part C (sequential combination therapy), and Part D (coadministration). Safety data from dose escalation phases will be summarized by dose, dosing regimen, and across all doses and dosing regimens. Safety data from dose expansion phases will be summarized for each disease cohort, overall by dose and dosing regimen, and across doses and dosing regimens, as appropriate. Efficacy data from dose expansion phases will be summarized for each disease cohort by dose and across doses. Efficacy data from dose escalation phases will be summarized by dose and listed by tumor type.

Descriptive statistics will include the number of observations and percentage in each category for categorical variables. For continuous variables, the number of observations, mean, median, standard deviation, minimum, and maximum will be presented unless otherwise specified. All available data will be included in-subject listings.

### **8.4.1 *Demographics and Baseline Characteristics***

Frequency distributions of gender, race, ethnicity, and other categorical baseline characteristics will be tabulated. Baseline body mass index (BMI) will be derived from measurements of baseline body weight and height. Summary statistics for age, body weight, height, and BMI will be

tabulated. Baseline disease characteristics will be summarized for expansion cohorts for different disease cohorts separately, as appropriate.

#### **8.4.2 Efficacy Analyses**

Individual BOR, DOR, and PFS will be determined based on RECIST v1.1 criteria for the primary and secondary analyses. iRECIST will be used as an exploratory analysis in Parts C and D. BOR outcomes will be summarized using frequency tables together with 2-sided 95% CIs. Time to event distribution (eg, PFS and DOR) will be estimated using the Kaplan-Meier method. When appropriate, the median along with 95% CI will be provided using Brookmeyer and Crowley methodology (using log-log transformation for constructing the CIs). Rates at fixed time points (eg, PFS rate 24 weeks) will be derived from the Kaplan-Meier estimate, and corresponding CI will be derived based on Greenwood formula. CIs for binomial proportions will be derived using the Clopper-Pearson method. OS data will be analysed similarly to PFS data analysis.

For the purpose of demonstrating preliminary clinical evidence of the treatment effect in advanced melanoma subjects who progressed while on receiving anti-PD-1 antibody therapies, the primary efficacy population will be subjects with LAG-3 expression who progressed while on anti-PD-1 antibody therapies in Part D1-Q2W. A portion of subjects in Part C who meet the eligibility criteria of Part D1 will be included in the sensitivity analysis to further strengthen the evidence. Efficacy analysis will also be performed for subjects with a lack of LAG-3 expression, and also for all treated subjects regardless of LAG-3 expression to support the treatment effect of the combination therapy.

Initial cutpoint for the purpose of exploring an enriched population is LAG-3 expression  $\geq 1\%$ . However, as the optimal marker cutpoint is not well known prior to the study, several different cutoffs may be explored other than the initial cutpoint of 1% by examining receiver operating characteristics curves using the ORR, although the decision of the cutpoint will be based on the totality of the efficacy data, including DOR and DCR. Details of methodology will be described in the statistical analysis plan prior to any data exploration in Part D.

In an effort to explore an enriched patient population in advanced melanoma subjects who progressed while on anti-PD-1 antibody therapies in Part D1, other potential predictive markers such as BRAF mutation status may be explored.

Subsequently, efficacy analysis for Part D1-Q4W will be done similarly to that for Part D1-Q2W. If the outcome of BOR in the Part D1-Q4W is deemed similar to that of the Part D1-Q2W, data from both Part D1-Q2W and Part D1-Q4W may be combined to strengthen the evidence.

Efficacy analysis for Part D2 will be done similarly to that for Part D1.

#### **8.4.3 Safety Analyses**

All subjects who receive study drug therapy will be evaluated for safety endpoints. All recorded AEs will be coded according to the most current version of MedDRA and will be graded using the NCI CTCAE v4.0. AEs will be listed and subjects with AEs will be summarized based on the event with worst CTCAE grade by system organ class (SOC) and PT, counting once at the PT term level and once at the SOC level, for each dose, dosing regimen, and overall. The incidence of AEs

in the Broad and Narrow Scope MedDRA Anaphylactic Reaction SMQ and select AEs in hypersensitivity/infusion reaction category occurring within 2 days after dosing by treatment arm, the difference in rates between arms, and the corresponding 95% CIs will be reported descriptively. The CIs for the rate estimates will be based on the Clopper-Pearson method. Vital signs and clinical laboratory test results will be listed and summarized by treatment. In addition, the worst grade of a laboratory measure observed on-study by the baseline grade (per CTCAE v4.0) will also be generated for selected laboratory tests. Any significant physical examination findings and results of clinical laboratory tests will be listed. ECG results will be evaluated by the Investigator, and abnormalities, if present, will be listed. In Parts A and B, ECG will be assessed by a central reader at specific time points. All ECG data analyses, including summaries of each ECG parameter, frequency distributions of subjects' maximum values/changes, and scatter plots, will be performed following the current practice of ECG data analysis. Concentration-response analysis may be performed using mixed-effect model, if appropriate. The details of ECG data analysis will be provided in the statistical analysis plan.

#### **8.4.4 Pharmacokinetic Analyses**

[figure not shown]
Pharmacokinetic parameters for BMS-986016 will be calculated using noncompartmental analyses. Summary statistics will be tabulated for the PK parameters of BMS-986016 by dose and study day/cycle. To describe the association of these parameters with dose of BMS-986016, scatter plots of Cmax and AUC(TAU) vs dose may be provided for each day/cycle measured. Dose proportionality of BMS-986016 when administered alone or coadministered with nivolumab may also be assessed based on a power model. Trough concentrations of BMS-986016 will be plotted vs study day and cycle. Nivolumab end-of-infusion and trough (Ctrough) concentrations will be tabulated using summary statistics. These data may also be pooled with other datasets for population PK analysis, which will be presented in a separate report. In Part D1-Q4W, PK comparisons will be summarized using descriptive summary statistics, and the point estimate and CI of geometric mean ratios of Cmax and AUC(TAU) will be presented to compare nivolumab and BMS-986016 administered as FDC to that of coadministered nivolumab and BMS-986016. PK parameters will also be summarized using descriptive summary statistics for nivolumab and BMS-986016 administered in Part D1-Q2W and Part D1-Q4W dosing.

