#### **1.1.9.1 Rationale for Flat Dosing**

Therapeutic mAbs doses have been routinely calculated on a body size basis with a perception that this approach may reduce intersubject variability in drug exposure compared with a flat dose approach. However, recent analyses of marketed and experimental mAbs have demonstrated that body weight-based dosing did not always offer advantages over flat dosing in reducing exposure variability. Since the magnitude of the impact of body weight on the human PK of BMS-986016 is not yet determined and it is unknown if body size-based dosing would increase or decrease intersubject variability, this study will utilize a flat dose escalation and expansion since it is the simpler of the 2 approaches and may result in fewer dosing errors. The impact of body weight on the PK of nivolumab is small, and the dose-response relationship is relatively shallow near the 3-mg/kg dose level, indicating that nivolumab can also be administered as a flat dose in combination with BMS-986016 in this study.

Flat doses for this study have been normalized for an average 80-kg adult cancer patient. A dataset from the nivolumab program used for preliminary population PK contained 325 subjects with a median weight of 81 kg. This value aligns well with a study by Bai et al, which found a median weight of 78 kg in 2519 adult patients with rheumatoid arthritis, breast cancer, colorectal cancer, NSCLC, ovarian cancer, and non-Hodgkin's lymphoma.

Additionally, BMS-986016 flat dose of 20 to 800 mg as monotherapy and up to 480 mg in combination with nivolumab (both given Q2W) has been studied across the 40 to 120 kg weight range in adults.

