#### **1.4.1.4 Clinical Pharmacology and Safety**

##### **1.4.1.4.1 Clinical Pharmacology**

Relatlimab PK was well described by a 2-compartment model with time-varying linear and nonlinear clearance. The time-varying linear clearance was described by an empirical Emax model. The baseline covariate effects of body weight, sex, albumin, and lactate dehydrogenase (LDH) on baseline clearance and body weight on central volume of distribution were found to be statistically significant. The baseline covariate effects of race, age, ECOG PS, hepatic function, renal function, tumor type, and coadministration with nivolumab on relatlimab PK were not statistically significant.

[REDACTED]

Currently available data suggest that the immunogenicity rate of anti-relatlimab antibodies is approximately 7% and 21% when administered alone and in combination with nivolumab, respectively. A neutralizing antibody assay is currently being developed to further assess neutralizing potential of anti-relatlimab antibodies. The clinical significance of immunogenicity will be assessed using all available data on efficacy, safety, and time of immunogenicity occurrence.

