**Table 8.1.4.2-1: 95% CI for Rate Differences When Observed in 75 Subjects per Arm and 150 Subjects per Dosing Regimen**

75 Subjects per Arm		
Coadministration Arm	Fixed Dose Combination Arm	Rate Difference (95% CI)
14%	14%	0% (-11.1%, 11.1%)
14%	12%	2% (-8.8%, 12.8%)
16%	14%	2% (-9.4%, 13.4%)
18%	16%	2% (-10%, 14%)
20%	18%	2% (-10.6%, 14.6%)
150 Subjects Each in Part D1-Q4W and Part D1-Q2W		
Q2W	Q4W	Rate Difference (95% CI)
14%	14%	0% (-7.9%, 7.9%)
14%	12%	2% (-5.6%, 9.6%)
16%	14%	2% (-6.1%, 10.1%)
18%	16%	2% (-6.5%, 10.5%)
20%	18%	2% (-6.9%, 10.9%)

Also, with 75 subjects per arm, there is a 99% probability that the 95% CI for the geometric mean ratio of Cmax of FDC to coadministration is wholly contained within [0.8, 1.25]. log(Cmax) is assumed to follow a normal distribution and, with intrasubject coefficients of variation, is assumed to be no greater than 30%.

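### The relatlimab Cmax ratio of FDC to coadministration is planned without body-weight adjustment, which gives up precision that the baseline data could supply

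*Combined protocol and SAP*

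**What the plan says.** Section 8.4.4 of the protocol states that in Part D1-Q4W "the point estimate and CI of geometric mean ratios of Cmax and AUC(TAU) will be presented to compare nivolumab and BMS-986016 administered as FDC" to coadministration, alongside descriptive statistics. It specifies no regression model and no covariate. It adds that the data may be pooled for a population PK analysis in a separate report, but does not tie that analysis to this ratio.

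Section 3.1.2.5 makes the two arms (coadministration and FDC, both 160 mg relatlimab with 480 mg nivolumab Q4W) separate randomized arms, so no subject acts as their own control. Dosing is flat, except that adolescents under 40 kg are dosed per kilogram (Section 1.1.9.8).

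On body weight, Section 1.4.1.4.1 says of relatlimab: "The baseline covariate effects of body weight, sex, albumin, and lactate dehydrogenase (LDH) on baseline clearance and body weight on central volume of distribution" were statistically significant. It gives no effect size. Section 1.1.9.1 says the flat doses studied so far cover a wide range of body size (relatlimab "has been studied across the 40 to 120 kg weight range in adults", for Q2W regimens). The same section still describes the weight effect on relatlimab as undetermined, and calls the effect on nivolumab small.

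The text under Table 8.1.4.2-1 gives the precision target: "with 75 subjects per arm, there is a 99% probability that the 95% CI for the geometric mean ratio of Cmax" of FDC to coadministration lies inside 0.80 to 1.25. It takes log(Cmax) as normal and a CV that, labelled as intrasubject, "is assumed to be no greater than 30" per cent.

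**The concern.** With a fixed milligram dose, concentration at the end of the infusion depends on central volume, and central volume depends on weight. In a parallel comparison the spread of body weight therefore enters the residual variance of log(Cmax) and widens the interval around the ratio. Weight is measured at screening (Table 5.1-1) and tabulated (Section 8.4.1), so this part of the variance could be removed without collecting anything new.

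What is at stake is the width of one reported interval for a secondary objective (Section 1.3.2). The interval does have a precision target attached to it, so its width is something the plan itself treats as relevant.

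**Working it through.** **1. Reproduce the plan's 99%.** Inputs from the text under Table 8.1.4.2-1: 75 per arm, CV 30%, limits 0.80 and 1.25, 95% CI. A true ratio of 1.00 is assumed, because none is stated.
- SD of log(Cmax) = sqrt(ln(1 + 0.30²)) = sqrt(0.0862) = 0.2936.
- Standard error of the log ratio = 0.2936 × sqrt(2/75) = 0.0479.
- Two one-sided tests at 0.025 each, t with 148 df, averaged over the distribution of the variance estimate: probability 99.2%. The stated 99% is reproduced.

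**2. Inputs for the weight effect (all assumed; the documents give none).**
- SD of log weight: 0.22 (range 0.18 to 0.26).
- Cmax proportional to weight to the power -0.65 (range 0.5 to 0.8 in size).
- Total CV: 30% and 40%. The 30% is the plan's figure. The 40% is shown because that figure is labelled intrasubject, whereas a parallel comparison carries between-subject variability as well. Log variance is 0.0862 at 30% and 0.1484 at 40%.

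**3. Share of log-Cmax variance due to weight** = (exponent × SD of log weight)² / log variance.
- Central: (0.65 × 0.22)² = 0.0204. Share = 0.0204/0.0862 = 24% at CV 30%, and 0.0204/0.1484 = 14% at CV 40%.
- Extremes: (0.5 × 0.18)²/0.1484 = 5%, and (0.8 × 0.26)²/0.0862 = 50%.

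**4. Narrowing of the interval on the log scale** = 1 - sqrt(1 - share).
- Central: 13% at CV 30% and 7% at CV 40%.
- Extremes: about 3% and 29%.
- The central gain equals that from 1/(1 - share) - 1 = 31% or 16% more subjects.

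**5. What this does to the plan's own criterion** (step 1 repeated with the reduced variance and 147 df).

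| Total CV | Unadjusted | Adjusted, central | Adjusted, range |
|---|---|---|---|
| 30% | 99.2% | 99.9% | 99.6% to nearly 100% |
| 40% | 88.2% | 93.3% | 90.4% to 97.4% |

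The typical 95% interval at CV 30% goes from the ratio ×/÷ 1.099 to ×/÷ 1.086.

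**6. Chance imbalance.** A one-SD chance difference in mean log weight moves the log ratio by 0.65 × 0.22 × sqrt(2/75) = 0.023, or about 2.3%. This is the same variance component as in step 4, seen from another side. It is not a second loss.

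**7. AUC(TAU).** Serial relatlimab samples are scheduled only for the first 12 subjects of Arms 2 and 3 (Table 5.5.1-5). The table does not make clear whether that is 12 per arm or 12 in total. Later subjects have predose and end-of-infusion samples only (Table 5.5.1-4). If AUC also has a CV of 30% (an assumption), the unadjusted interval is ×/÷ 1.28 with 12 per arm and ×/÷ 1.46 with 6 per arm, both already wider than 0.80 to 1.25. One covariate takes the residual df from 22 to 21 (t from 2.074 to 2.080) or from 10 to 9 (t from 2.228 to 2.262). No narrowing is quoted for AUC, because AUC depends on clearance and the Cmax exponent cannot be borrowed for it.

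**The case against.** The strongest reply is that this is an efficiency point on a secondary, descriptive output. The primary D1-Q4W endpoint is the anaphylactic-reaction SMQ rate, Section 1.2 says no prospective hypotheses are formally evaluated, and Section 8.4.4 attaches no decision rule to the ratio. Randomized arms give an unbiased ratio, and the unadjusted interval already covers chance weight imbalance. At the plan's own 30% CV the containment probability is 99.2% before any adjustment. All of this stands, and it limits how much weight the point deserves.

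A second reply is that silence in Section 8.4.4 is not proof that no adjustment is planned. The protocol refers elsewhere to a statistical analysis plan, which might supply a model. That also stands as a caveat, but nothing in the text reviewed does so, and the population PK analysis is optional and separate.

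A reader might infer three stronger claims.
- **That the ratio is biased by body size.** It is not among randomized subjects. The documents do leave open whether the up to 9 FDC lead-in subjects treated before randomization (Section 3.1.2.5) enter the comparison. That is a question about the analysis set, not evidence of bias.
- **That adjustment would rescue AUC(TAU).** The limit there is sparse sampling, and the loss of a degree of freedom begins to matter.
- **That nivolumab needs the same treatment.** Section 1.1.9.1 calls its weight effect small, and Table 5.5.1-5 schedules no nivolumab sample between the end of infusion and Day 29 predose, even in the first 12 subjects.

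**Conclusion.** The point holds for relatlimab Cmax, as a loss of precision. The plan names weight as a driver of relatlimab central volume, collects it, and then specifies a between-arm comparison that does not use it. Adjustment would narrow the interval by about 7-13%, or about 3-29% over the wider assumptions. These sizes rest on an assumed spread of weight, weight exponent and total CV, none of which the documents supply. If total CV really is 30%, the practical consequence is slight. If it is nearer 40%, adjustment recovers about 5 percentage points of containment probability (88.2% to 93.3%) under the central assumptions. The conclusion does not extend to bias in the randomized comparison, to nivolumab, or to AUC(TAU) as a main analysis.

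**What to change.** In Section 8.4.4, or in the statistical analysis plan it relies on:
- Estimate the relatlimab Cmax geometric mean ratio and its 95% CI from a linear model on log(Cmax) with arm and log baseline body weight. Present this as the main descriptive result, with the unadjusted ratio as supportive.
- Exclude subjects dosed per kilogram from the ratio, or account for their actual dose in the model.
- For relatlimab AUC(TAU) and for the nivolumab ratios, give a weight-adjusted estimate only as a sensitivity analysis. State how many subjects per arm contribute to AUC(TAU).

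The cost is a few lines of text and one model. No new data are needed. One degree of freedom is spent, which is negligible with 75 per arm and matters only in the 12-subject AUC subset. If the unadjusted ratio has already been produced, the adjusted one should be labelled post hoc.
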